1.2 Mucositis

Oral mucositis, ulceration of the oral mucosa, is one of the major and frequent complications of radiation and chemotherapy in head and neck cancer patients[12, 13]. A combination of dose-related chemoradiation epithelial damage, micro-vascular injury, elevated release of cytokines such as TNF- α , and oxidative stress with subsequent generation of reactive oxygen species contribute to the development of oral mucositis[12, 14]. Recent data suggests that occurrence of severe oral mucositis occurs in up to 66-85% of patient's [15, 16]. Development of mucositis is accompanied with severe pain [13, 17]. Mucositis associated pain has a mixed pathogenesis which includes both somatic and neuropathic components. The pain symptoms usually begin two to three weeks after the start of chemoradiation therapy and are at its worst at the completion of therapy. Development of mucositis in cancer patients has significant impacts on health, quality of life, and recovery [14, 17]. Associated pain results in dysphagia making it difficult for patients to eat and thus increasing their risk for weight loss and volume contraction dehydration throughout therapy as well precipitates the need for parenteral nutrition[12, 18]. Furthermore, erosive mucositis puts patients at risk for development of secondary infection and sepsis especially in the presence of concurrent neutropenia [14]. Severe mucositis may require a dose reduction during therapy, altering the course of Chemoradiotherapy originally set forth.

Current treatment of mucositis includes symptom management with routine oral care, mucosal coating agents, chlorhexidine, both topical and systemic analgesics, and oral cryotherapy[15, 16, 18]. Systemic analgesics commonly used for treatment include opioids, non-steroidal anti-inflammatory agents, and acetaminophen[15]. Because of issues with dysphagia, oral administration of analgesics may be hampered. Thus, transdermal formulations are frequently utilized. Unfortunately, opioids are associated with well-documented side effects (e.g. addiction, tolerance, and dependence) and are frequently ineffective for controlling mucositis associated pain [19]. Thus, a search for other pain medications to manage mucositis induced pain is of clinical importance. Since peripheral sensitization is one of the underlying

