3.0 Inclusion/Exclusion Criteria

Inclusion Criteria

- Histologically proven cancer of the head and neck cancer
- Stage 3 or 4 under the AJCC and IUCC staging System OR patients with Stage 1 or 2 disease who will receive radiation equivalent to patients with Stage 3 or 4 disease
- Planned primary or adjuvant chemoradiation therapy
- Willing and able to provide informed consent
- Age \geq 21 years
- English speaking

Exclusion Criteria

- Currently on gabapentin
- Prior non-tolerance of gabapentin
- History of seizure disorder

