- Patients who are tolerating the current dosing schedule will undertake an escalation to the next dose level.
- If patients have mild to moderate side effects related to gabapentin, no further dose escalation will be undertaken
- If patients develop severe side effects attributable to gabapentin, gabapentin will be held until the side effects have totally resolved and then restarted at the last known tolerated dose level.
- Although rare, severe mood alterations and suicidal thoughts have been associated with this agent. Should patients experience these symptoms, gabapentin will be permanently discontinued.

5.4 Route of Administration:

Gabapentin is usually taken orally. Gabapentin may also be crushed and given via feeding tube if the patient is unable to swallow the tablet.

5.5 Pain Management:

Pain management for tumor and treatment related toxicities will be at the discretion of the treating physician. Opioid and adjuvant use will be documented for study purposes. At the completion of study, patients on Arm 1 may be started on gabapentin if they have uncontrolled mucositis associated pain. For patients assigned to Arm 1, the treating physician will manage the utilization of gabapentin during the post-treatment phase

5.6 Study Visits:

In order to minimize inconvenience to patients under study, study visits will coincide with scheduled treatment. This may introduce a degree of variability in the timing of weekly visits and follow-up visits which will be considered acceptable except in cases where explicit visit timing is dictated elsewhere in the protocol. Weekly on treatment visits that are more than 1 week late will be considered missing.

Baseline:

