Prior to initiating therapy, patients will undergo education sessions with study staff. The educational intervention will include a discussion of oral health foundations as well as a discussion of pain management. This education is standardly applied to all VUMC patients undergoing radiation therapy for HNC and will not be otherwise documented. In addition, patients will also be given written material to review. Patient will be given a pain diary and instructed on its use. Baseline pain medication use will be documented. Patients will complete the demographic survey. Patients randomized to gabapentin will be given a prescription for gabapentin with dose escalation as noted in the treatment section. Patients who do not have insurance or who are unable to afford gabapentin will be provided with medication from the indigent pharmacy. All baseline assessments must be done within 4 weeks of starting concurrent chemoradiation.

Weekly On Treatment Visits:

Starting with the initiation of concurrent chemoradiation, patients will be evaluated on a weekly basis. The evaluation will include:

- 1) review of the weekly pain survey
- 2) for patients on gabapentin (Arm 2) --we will review their compliance log and identify any barriers to compliance and strategies to improve their compliance
- 3) adjustment of pain regimen
- 4) completion and review of the Vanderbilt head and neck symptom survey
- 5) mucositis grading.

End-of-Treatment Visit:

Patients will undergo an evaluation at their final radiotherapy visit or within 2 weeks after. This will include the following:

- 1) review of the monthly diary survey
- 2) for patients on gabapentin (Arm 2) --we will review their compliance log and identify any barriers to compliance and strategies to improve their compliance

- 3) adjustment of pain regimen
- 4) completion and review of the Vanderbilt head and neck symptom survey
- 5) mucositis grading.

6.0 Study Measures:

6.1 Mucositis Grading:

Patients will have an oral exam twice a week as part of standard of care. Mucositis will be graded based on the World Health Organization criteria. Mucositis assessments will be done by trained study staff.

6.2 Patient Reported Outcome Measures:

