Study Visit: The study nurse will meet with the patient at baseline, weekly during radiation therapy, and at 1, 2 and 3 months post-treatment. At each study visit the study nurse will 1) administer appropriate questionnaires, 2) review the patient's pain diary and compliance diary, 3) document concurrent medications, 4) document toxicities based on CT CAE criteria 4.0, 5) identify and prepare reports for any adverse events, 6) document any dose adjustments in pain medications as recommended by the physician or nurse practitioner, and 7) educate the patient regarding medication dose and schedule.

As these patient reported outcome measures represent outcomes of interest for the study, they will not be altered by study staff due to missingness as changes would threaten the validity of the tool.

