Analyses for study aims. Graphical and descriptive statistical summaries will be generated for all study variables. Evaluation of the key outcome variable data distributions (VHNSS mouth pain scores, opioid dose) will inform the required test distribution (e.g., normal, log-normal). Mixed-level general linear modeling will be used to test study hypotheses. Given that patients will have varying VHNSS pain scores prior to beginning radiation, those baseline values will be included as a covariate in the analyses of outcomes [EOT: VHNSS pain scores (H1.1); opioid use (H1.2); weight loss (H2.1); duration of PEG (H2.2); general symptoms (Aim 4)]. Frequency distributions will summarize the safety and tolerability outcomes (Aim 3). All tests of statistical significance will maintain maximum Type I error of 0.05 ($p < 0.05$).

Sample size justification. The proposed sample size was based on typical VHNSS pain score values during/end-of-treatment in prior studies (M=4.5, SD=2.8). A total sample size of 120 patients (60 per arm) who complete the protocol will provide 80% statistical power (2-tailed alpha=0.05) to detect a decrease of 1.5 points on the VHNSS pain scale due to the addition of gabapentin to usual care. Given a change of 2.0 points on the scale is proposed to be clinically meaningful, this slightly larger sample size will provide coverage in the case that our sample values are slightly more variable than those observed in our prior studies. A total sample size of 120 will also enable us to detect correlations as small 0.25(6.3% shared variance) with 80% power and 2-tailed alpha=0.05. We expect clinically meaningful associations to be larger than this value.

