Appendix C: Pain Diary:

Date:

Please rate the following on a scale of 0-10 with 0 being no pain and 10 being the worst pain you have ever experienced:

1) What is your current pain level?

No Pain Worst Pain

0 1 2 3 4 5 6 7 8 9 10

2) What has been your average pain level this past week?

No Pain Worst Pain

0 1 2 3 4 5 6 7 8 9 10

3) What has been your worst pain level this week?

No Pain Worst Pain

0 1 2 3 4 5 6 7 8 9 10

4) On average, how many breakthrough doses of pain medication have you taken a daily?

5) Do you feel that your current pain regimen is appropriately controlling your pain?

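### Opioid use (H1.2) is adjusted for baseline pain but not for baseline opioid use; adding it is a cheap, low-priority precision gain of unknown, possibly near-nil, size

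*Combined protocol and SAP*

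**What the plan says.** The analysis paragraph of section 10.0 gives one adjustment rule. Its reason is that "patients will have varying VHNSS pain scores prior to beginning radiation", and it continues: "those baseline values will be included as a covariate in the analyses of outcomes [EOT: VHNSS pain scores (H1.1); opioid use (H1.2"). The values meant are the VHNSS pain scores. The same covariate serves pain, opioid use, weight loss, PEG duration and general symptoms, and no other covariate is named.

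Hypothesis 1.2 (section 2.0) concerns a 20% reduction in opioid use, in morphine equivalents, at week six.

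On what is collected before treatment, the baseline part of section 5.6 says "Baseline pain medication use will be documented". Section 6.2 has the study nurse "document concurrent medications" at each study visit, and baseline is one of those visits.

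**The concern.** H1.1 is adjusted for its own baseline and H1.2 is not, although the plan's reason for adjusting applies equally to analgesic use before radiation. A pain score is an imperfect stand-in for dose: a patient whose tumour pain is controlled by opioids can enter with a low score.

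Some opioid use at entry is plausible. Section 3.0 admits patients with "Planned primary or adjuvant chemoradiation therapy" and does not exclude opioid users, and section 5.5 says "Pain management for tumor and treatment related toxicities will be at the discretion of the treating physician". Section 4.0 describes permuted blocks and names no stratification factor, so the design does not balance baseline opioid use between the arms.

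At stake are the standard error of the H1.2 comparison and its protection against a chance imbalance.

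**Working it through.** **Inputs from the plan (section 10.0).** 120 completers, 60 per arm, two-sided alpha 0.05. The plan gives no SD for opioid dose, no share of patients on opioids at entry, no correlation between baseline and later dose, and no power for H1.2. Every correlation and share below is an assumption.

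**The plan's own figure, for pain only.** With a difference of 1.5 and an SD of 2.8, the normal formula gives 2 × (1.960 + 0.842)² × 2.8² / 1.5² = 54.7, so 55 per arm. At 60 per arm power is 83.5%, against 80% stated. The plan explains the surplus as cover for a larger SD. This fixes N and has no other bearing on H1.2.

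**1. Gain from the added covariate.** Let ρ be the partial correlation of baseline opioid use with the outcome, given baseline pain. In a linear model the variance of the arm effect is multiplied by (1 − ρ²). One extra parameter costs a factor of about 1 + 1/115 = 1.009. Effective N is 120/(1 − ρ²).

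| ρ | variance reduction before the parameter cost | effective N |
|---|---|---|
| 0 | 0% | 120 |
| 0.1 | 1% | 121 |
| 0.2 | 4% | 125 |
| 0.3 | 9% | 132 |
| 0.5 | 25% | 160 |
| 0.7 | 51% | 235 |

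Break-even is at ρ² = 1/116, so ρ of about 0.09. Net of the cost, the gain at ρ = 0.5 is 1 − 0.75 × 1.0087 = 24%.

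**2. How far baseline pain may already do the work.** Let r be the correlation of baseline dose with the outcome, a that of pain with the outcome, and b that of pain with baseline dose. Then ρ = (r − ab) / √[(1 − a²)(1 − b²)].

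- a = b = 0.3: ρ² is 5%, 20% and 45% at r = 0.3, 0.5 and 0.7.
- a = 0.5, b = 0.6: ρ² is 0% at r = 0.3 and 8% at r = 0.5, where ρ = 0.20/0.693 = 0.289.

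**3. If few patients use opioids at entry.** Suppose only yes/no use is known and users are those above a cut-off on a normal scale, with share p. Then r and b both shrink by φ(z)/√[p(1 − p)], where z is the cut-off and φ the normal density. At p = 10% the factor is 0.1755/0.30 = 0.585. With a = b = 0.3 before shrinkage, the net change in variance is a 0.9% loss at r = 0.1, a 0.9% gain at r = 0.3, and gains of about 6% at r = 0.5 and 14% at r = 0.7.

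A simulation with dose known agrees for weak correlations. It used 60 per arm, 90% opioid-free at entry, log-SD 0.8, 10% zero doses at the outcome, and both pain correlations at 0.3. It ran from a 2% loss to a 3% gain for correlations of 0.1 to 0.3.

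**4. Chance imbalance.** The 95% range for the between-arm difference in the share of baseline users is ±1.96 × √[2p(1 − p)/60]: ±10.7 points at p = 10%, ±15.5 at 25% and ±17.9 at 50%.

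**5. Why absolute power cannot be stated.** Take a ratio of 0.80, a model on log dose with no zeros, and pain as the only covariate (a = 0.3). The standard error is SD × √0.91 × √(2/60), and power is Φ(0.223/SE − 1.96). A log-SD of 0.8 gives SE 0.139 and 36% power; a log-SD of 0.5 gives SE 0.087 and 73%. Adding baseline dose (b = 0.3) at r = 0.5 and 0.7 gives 43% and 58% in the first case, and 82% and 93% in the second. The documents do not choose between these.

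**The case against.** The strongest reply is that a valid analysis without an optional covariate is not an error, and that the documents' one statement on timing points to little gain: "The pain symptoms usually begin two to three weeks after the start of chemoradiation therapy". Many patients may then enter opioid-free. This stands, and it is why the point ranks low.

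The baseline record may also hold no dose. The demographic form has no medication item. The pain diary asks "On average, how many breakthrough doses of pain medication have you taken a daily", which is a count, and both calendars start the pain survey at week 1. VHNSS item 27 has a box for patients on no pain medication, but it covers any analgesic, and neither calendar marks VHNSS at baseline. This stands too: the cost is low only if the medication record yields drug, strength and frequency, or at least yes/no opioid use.

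The plan calls for mixed-level general linear modelling. If baseline opioid use entered as a repeated measure, its information would already be used. The documents neither say nor exclude this, and the calculations above are for a single time point.

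Two stronger readings are tempting. A reader might infer that leaving out the covariate biases H1.2; randomisation rules that out. A reader might also infer a definite power, for instance that H1.2 stays under 40% with or without the covariate, or that the covariate rescues it. Either depends on an SD that the plan does not give.

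**Conclusion.** The point holds as a cheap improvement of low priority. H1.2 is adjusted for baseline pain only, although baseline pain medication must be documented. The planned test remains valid; the possible loss is in precision and in protection against chance imbalance.

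The size is unknown. It lies between a loss of about 1% to 2% of variance, if the covariate is uninformative, and a gain that becomes material (about 25%) only at an assumed partial correlation of about 0.5 or more. Few opioid users at entry with a weak link to later dose, or a pain score that already carries the information, would put it near nil. The case for acting is the small cost and the need to settle covariates before outcomes are seen, not an expected large gain.

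**What to change.** Before any outcome data are inspected:

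1. Check whether the baseline medication record holds drug, strength and frequency.
2. Add baseline opioid use to the H1.2 model beside baseline VHNSS pain: baseline morphine equivalents if they can be derived, otherwise any opioid use yes/no.
3. State the functional form in the SAP. If both an any-use indicator and a dose term are used, that is two parameters.

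The planned general linear model can stay. The cost is one line in the SAP, the record check, and about 0.9% of variance per added parameter if the covariate carries no information, so about 1.8% for two.

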hypothesized to improve not only pain but also improve quality of life parameters such as swallowing and nutritional intake.

A retrospective study evaluated this question. Investigators conducted a chart review of 42 patients with head and neck malignancies treated with concurrent chemoradiotherapy using an intensity-modulated radiotherapy technique. Pain outcomes for patients treated with gabapentin for prevention of mucositis associated pain were compared to pain outcomes for patients using standard supportive care. Results found that preventive administration of gabapentin reduced overall pain levels and the total dose of opioids utilized [34]. Although the data is intriguing, there are numerous limitations to this study. First, the study was retrospective. Second, patients were not randomized and third, outcomes were not pre-established. None-the-less, the data would support further investigation of gabapentin as chronic preventive measures for mucositis associated pain in patients undergoing chemoradiation for head and neck cancer

1.6 Study Summary:

The overall goal of this study is to determine whether or not Gabapentin can reduce mucositis associated pain in head and neck cancer patients undergoing chemoradiation. Patients seen in the Oncology Clinic for routine surveillance will be informed about the study and asked if they interested in participation. Interested patients will be asked to sign an informed consent. They will then be randomized into to two arms—standard of care and standard of care plus gabapentin. Prior to chemoradiation therapy, subjects will undergo education on chemoradiation as well as foundations of oral care. Subjects will be asked to complete a demographic survey, the Head and Neck Symptom Survey 2.0 plus the General Symptom Survey (VHNSS v2.0 plus GSS), the Profile of Mood States – short form (POMS-SF), the Neurotoxicity Rating Scale (NRS), the and a Quality of Life (QOL) assessment as outlined below. Subjects will also be requested to maintain a pain diary that will be used throughout the study to assess their pain and their mucositis will be graded weekly during their visits.

Upon completion of therapy, the data will be collected and stored in a secure password protected database and the patient's study participation will end. We anticipate the study duration to be 2 years.

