2.0 Specific Aims

Specific Aim 1: To determine whether Gabapentin used as a preventive measure during chemoradiation can reduce radiation-induced mucositis associated pain in head and neck cancer patients as measured by: 1) pain scores on the Vanderbilt Head and Neck Symptom Survey (VHNSS version 2.), and 2) analgesic use.

Hypothesis 1.1: Compared to controls, patients using Gabapentin during radiation-based therapy will have a 1.5 point decreases in self-reported oropharyngeal pain (on a scale of 0 to 10) week six of radiation.

Hypothesis 1.2: Compared to controls, patients using Gabapentin during radiation-based therapy will have a 20% decrease in opioid use (as measured in morphine equivalents) at week six of radiation.

Specific Aim 2: To determine whether pain control is associated with weight loss (in pounds) and duration of use of percutaneous endoscopic gastrostomy utilization (in days).

Hypothesis 2.1 Patients with less pain will have decrease weight loss.

Hypothesis 2.2 Patients with less pain will have a shorter duration of PEG placement.

Specific Aim 3: To assess the safety (grade 3 or 4 adverse events) and tolerability of using gabapentin (discontinuation of drug due to side effects - yes or no).

Specific Aim 4: To correlate pain severity with frequency and severity of general systemic symptoms.

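### H2.1 (weight loss in pounds) and Aim 4 (general symptoms) are adjusted for baseline pain only; adding each outcome's own baseline is a nearly free improvement

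*Combined protocol and SAP*

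**What the plan says.** Section 10.0, under the analyses for study aims, notes that VHNSS pain scores will differ between patients before radiation and states that "those baseline values will be included as a covariate in the analyses of outcomes". The word 'those' refers to VHNSS pain scores. The outcomes that receive this covariate include "weight loss (H2.1); duration of PEG (H2.2); general symptoms (Aim 4"). The model is given in one sentence, "Mixed-level general linear modeling will be used to test study hypotheses", and no further covariate is named anywhere.

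Section 2.0 frames both aims as associations with pain, not as comparisons of arms. Aim 2 concerns "weight loss (in pounds"), and H2.1 predicts less loss in patients with less pain. Aim 4 is "To correlate pain severity with frequency and severity of general systemic symptoms", with no hypothesis attached.

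On whether the baselines are available, the documents disagree:

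- Section 1.6 lists "the Head and Neck Symptom Survey 2.0 plus the General Symptom Survey (VHNSS v2.0 plus GSS") among the surveys to be completed, directly after a sentence about the period before chemoradiation.
- Both copies of the Appendix I calendar leave the baseline cell of the VHNSS row empty.
- The baseline visit text in section 5.6 does not list the survey.
- Neither calendar has a row for weight, and no form in the appendices has a field for measured weight.

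**The concern.** The plan adjusts pain for its own baseline because patients differ before radiation. The same reason applies to general symptoms and to body weight, yet those outcomes are adjusted for the baseline of a different variable.

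**H2.1.** At the same percent loss, a heavier patient loses more pounds: 10% is 13 lb at 130 lb and 25 lb at 250 lb. That spread has nothing to do with pain. It adds noise to the outcome and dilutes any association with pain.

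**Aim 4.** Pain (items 22-28) and general symptoms (items 51-61) sit on the same Appendix B form, with the same 0-10 format and one-week recall. A patient who reports much fatigue, poor sleep or low mood before radiation may report more of both later. Without baseline general symptoms, a correlation at the end of treatment cannot be read as having arisen since radiation began.

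**Working it through.** **Inputs from section 10.0.** N = 120, two-sided alpha 0.05, detectable correlation 0.25 with 80% power. The documents give no correlations among symptoms and no weight data, so every other input below is an assumption.

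**The plan's own figure.** By Fisher's z with k covariates, power = Φ(atanh(r)·√(N − 3 − k) − 1.96). With r = 0.25 and k = 0, this is Φ(0.2554 × 10.817 − 1.96) = Φ(0.80) = 78.9%. The smallest correlation with 80% power is 0.253. The stated figure is reproduced to within about a point.

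**Cost of adjustment.** At r = 0.25, power is 78.6% with one covariate and 78.2% with two.

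**H2.1.** Assume that pain is related to percent loss and is independent of starting weight. Pounds lost = weight × percent lost. With mean loss m, SD of loss s and coefficient of variation of weight c,

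r(pounds) = r(percent) × s / √(s² + m²c² + c²s²).

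- Mildest case (m = 6%, s = 5 points, c = 15%): factor 0.974, so 0.25 becomes 0.24.
- Strongest case (m = 10%, s = 3 points, c = 25%): factor 0.754, so 0.25 becomes 0.19.
- A middle case (weight 180 lb, SD 40; loss 9%, SD 5 points): 0.25 × 900/√(900² + 360² + 200²) = 0.227, with power Φ(0.2314 × 10.817 − 1.96) = 71%.

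A simulation of 2,000,000 draws per scenario (m 6-10%, s 3-5 points, c 15-25%) gave:

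| Analysis | Correlation with pain | Power, N = 120 |
|---|---|---|
| Percent loss | 0.25 | 79% |
| Pounds, no weight covariate | 0.19-0.24 | 54-77% |
| Pounds, baseline weight added | 0.24-0.25 | 76-78% |

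For stronger true associations, the middle-case factor 900/√(900² + 360² + 200²) = 0.909 and the same power formula give:

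| True r (percent loss) | r in pounds | Power, percent | Power, pounds |
|---|---|---|---|
| 0.25 | 0.227 | 79% | 71% |
| 0.28 | 0.255 | 88% | 80% |
| 0.30 | 0.273 | 92% | 86% |
| 0.35 | 0.318 | 98% | 95% |

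**Aim 4.** Suppose a shared reporting level is the only link between pain and general symptoms. All four scores (pain and symptoms, baseline and later) correlate at ρ, and each scale correlates with its own baseline at ρ + d. The partial correlation of later pain with later symptoms, given baseline pain, is

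[ρ − (ρ + d)ρ] / √{[1 − (ρ + d)²](1 − ρ²)}.

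With ρ = 0.3 and d = 0 this is 0.21/0.91 = 0.23. With d = 0.2 it is 0.15/√(0.75 × 0.91) = 0.18. Adding baseline symptoms when d = 0 gives ρ/(1 + 2ρ) = 0.3/1.6 = 0.19. The values for d = 0.2 come from inverting the correlation matrix.

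| ρ | d | Baseline pain only | Plus baseline symptoms |
|---|---|---|---|
| 0.1 | 0 | 0.09 | 0.08 |
| 0.1 | 0.2 | 0.07 | 0.06 |
| 0.3 | 0 | 0.23 | 0.19 |
| 0.3 | 0.2 | 0.18 | 0.11 |
| 0.5 | 0 | 0.33 | 0.25 |
| 0.5 | 0.2 | 0.24 | 0.13 |

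At ρ = 0.3, the chance of a significant result with no true link falls from 51-72% to 23-53%. Adjustment also sharpens the estimate. If baseline symptoms correlated 0.6-0.7 with later symptoms given baseline pain, residual symptom variance would fall by 0.6² to 0.7², or 36-49%.

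**The case against.** **Aim 4 asks only for a correlation.** It has no hypothesis and makes no claim that mucositis pain causes the symptoms. A correlation that partly predates radiation still answers it. This stands: a reader might infer that the Aim 4 analysis is confounded and therefore invalid, and the text does not support that. What is lost is the reading that the association arose during treatment.

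**Adjustment may not remove the effect of reporting level.** A reader might infer that one extra covariate cures the problem. That would be so only if baseline symptoms carried all of the shared tendency. The table above drops that assumption, and much of the spurious correlation remains. This stands too.

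**The weight effect is modest.** Pounds are a prespecified, interpretable scale, and weight loss is already a change from baseline. The plan expects meaningful associations above 0.25, where power in pounds holds up better. The dilution also requires that pain acts on percent loss, which the documents do not establish. All of this is fair: the H2.1 point concerns precision, not bias. It still leaves no reason to omit a covariate that costs less than a point of power.

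**The baselines may not be collected.** The calendars show neither. But section 10.0 already requires baseline pain from the same form, and weight loss cannot be computed without a starting weight. The conflict needs an edit; it does not defeat the point.

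**Conclusion.** The omission is plain in section 10.0, and it affects two aims that randomisation does not protect. For H2.1 it dilutes a true correlation of 0.25 to about 0.19-0.24, with less loss of power if the association is stronger. For Aim 4 it leaves a partial correlation of 0.07-0.33 with no true link, a range that includes the plan's detectable 0.25, and adding baseline symptoms brings it to 0.06-0.25. The directions follow from the scale of the outcome and the shared form. The sizes rest on assumed weight, loss and correlation values and should be read as ranges.

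A reader might infer that the trial's main result is at risk. It is not: H1.1 compares randomised arms and is adjusted for its own baseline. The sample size rests on that comparison, and H2.1 and Aim 4 are secondary to it. This is a free improvement, not a flaw that threatens the trial.

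**What to change.** In section 10.0, under the analyses for study aims:

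- **H2.1:** keep pounds and add baseline weight as a covariate, or analyse percent change from baseline weight.
- **Aim 4:** add the baseline General Symptom Survey score alongside baseline pain. Report this with the plain correlation, so that the stated aim is still answered, and say that adjustment reduces but does not remove the effect of reporting level.

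In the same edit, reconcile section 1.6 with section 5.6 and both copies of the Appendix I calendar, so that the VHNSS with general symptoms is shown at baseline, and add a weight row that includes baseline. The baseline pain covariate already in the plan depends on the same survey entry.

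The cost is a sentence or two in the SAP, two calendar corrections and at most one extra covariate per model. Power at r = 0.25 stays within a point (78.9% to 78.2-78.6%). No visit is added.

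### Aim 3 is analysed by frequency distributions alone, with no between-arm estimate for grade 3 or 4 adverse events and no confidence interval for either safety outcome

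*Combined protocol and SAP*

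**What the plan says.** Section 2.0 sets the aim: "To assess the safety (grade 3 or 4 adverse events) and tolerability of using gabapentin (discontinuation of drug due to side effects", the latter recorded as yes or no. Unlike Aims 1 and 2, Aim 3 carries no hypothesis, and no margin is given.

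Section 10.0 assigns its method in one sentence: "Frequency distributions will summarize the safety and tolerability outcomes (Aim 3)". Two neighbouring statements might have added something but do not:

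- The general promise, "Graphical and descriptive statistical summaries will be generated for all study variables", names no contrast and no interval.
- The modelling is for testing study hypotheses. Its bracketed outcome list covers the pain score and then "opioid use (H1.2); weight loss (H2.1); duration of PEG (H2.2); general symptoms (Aim 4)". Aim 3 is not in it.

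Section 8.1 covers grading, review and reporting of adverse events and the role of the monitoring board. It contains no statistical comparison of harm. No confidence interval or risk difference is specified for any safety outcome anywhere in the documents.

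**The concern.** The patients are receiving a toxic treatment. Section 1.2 says that "occurrence of severe oral mucositis occurs in up to 66-85% of patient's", and Section 1.1 describes the toxicities of treatment as numerous and often severe. The frequency of severe events among patients taking gabapentin is therefore a mixture of drug effect and background. The randomised control arm is what separates the two, and the Aim 3 sentence does not say that it will be used for this.

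Percentages without intervals also hide imprecision. The trial was sized for a pain difference, so two similar-looking percentages could coexist with a sizeable true excess of severe events, and a reader of the planned tables would have no measure of it.

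**Working it through.** **Inputs from the documents**

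- Recruited: 150 (Section 4.0), so about 75 per arm at 1:1.
- Completing: 120, or 60 per arm (Section 10.0). The allowance is up to 20% lost, and 150 × (1 − 0.20) = 120, which reproduces.
- Intent-to-treat principles apply to all analyses (Section 10.0). That points to 75 per arm; 60 is the lower case if adverse event data exist only for completers.
- Toxicities are documented under CTCAE 4.0 at each study visit (Section 6.2), and all events of grade 3 or higher are documented (Section 8.1). Neither is restricted to one arm, so a between-arm estimate is feasible.

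**The plan's own figure.** The only power statement for a group comparison concerns pain: "A total sample size of 120 patients (60 per arm) who complete the protocol will provide 80% statistical power (2-tailed alpha=0.05)". With a 1.5-point difference and SD 2.8, 60 per arm gives 83.5% (normal approximation) or 82.9% (t distribution). The stated 80% is conservative, in line with the plan's remark that the sample is slightly larger to cover extra variability. No power or precision figure is stated for Aim 3.

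**Assumption.** The documents give neither an expected grade 3 or 4 rate nor an expected discontinuation rate. All rates below are assumed.

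**Step 1: severe events, equal observed rates.** If both arms show proportion p, the 95% half-width for the risk difference is 1.96 × √(2p(1 − p)/n). It is also the largest excess the interval would still allow.

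| p in both arms | n = 75 per arm | n = 60 per arm |
|---|---|---|
| 10% | 9.6 points | 10.7 points |
| 20% | 12.8 | 14.3 |
| 30% | 14.7 | 16.4 |
| 50% | 16.0 | 17.9 |
| 66% | 15.2 | 17.0 |
| 85% | 11.4 | 12.8 |

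For example, at p = 0.66 and n = 75: 1.96 × √(2 × 0.66 × 0.34/75) = 0.152. Newcombe intervals are close: 10.4 points for 8/75 in each arm and 15.6 for 38/75 in each arm.

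**Step 2: severe events, unequal rates.** With 22/75 against 15/75, the difference is 29.3% − 20.0% = 9.3 points, with a Newcombe 95% interval of −4.5 to +22.7.

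**Step 3: discontinuation, Arm 2 only, exact 95% intervals.** With zero events the upper limit is 1 − 0.025^(1/n): 4.8% for 0/75 and 6.0% for 0/60. For 8/75 the interval is 4.7% to 19.9%. For 15/75 it is 11.6% to 30.8%.

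**Step 4: would a single any-event count be enough?** If oral mucositis counts and 85% of patients qualify through it, only 100 − 85 = 15% of patients can still move the count through some other event. The plan grades mucositis on WHO criteria (Section 6.1) and adverse events on CTCAE 4.0 (Section 8.1), and does not say whether mucositis enters Aim 3. The contrast is therefore needed both with and without it.

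**Step 5: time window.** Section 5.5 allows Arm 1 patients to start gabapentin in the post-treatment phase. Section 6.2 schedules toxicity recording at 1, 2 and 3 months after treatment. A contrast that runs through those months could be diluted by Arm 1 exposure.

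**The case against.** Descriptive safety reporting is common, and Aim 3 is a secondary aim without a hypothesis in a trial sized for pain. Leaving out an interval biases nothing, does not touch type I error, and can be put right at reporting. Harm during the trial is reviewed by the study team and the monitoring board. All of this stands, and it limits the weight of the point.

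Four stronger readings are tempting, and the documents do not support them:

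- **That the trial cannot bound the harm.** Severe events are recorded in both arms, so counts and denominators would yield the interval later. The gap is in the planned output, not in the data.
- **That the arms will be pooled.** The plan does not say so. For a two-arm trial analysed by intent to treat, tables by assigned arm are the natural reading. What is missing is an explicit contrast and an interval.
- **That extra intolerance should be compared between arms.** Aim 3 defines tolerability as stopping the drug, and Arm 1 receives no study gabapentin. Only an Arm 2 proportion exists.
- **That 66-85% is this trial's severe event rate.** It is a literature figure, an upper range, for one toxicity. It serves here only as part of an assumed range.

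Nor do the documents commit to any favourable safety conclusion, so a misleading claim is a risk and not something planned.

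**Conclusion.** The point holds as a minor one. Frequency distributions are the whole of the stated Aim 3 analysis, and the output as planned would not show what excess of severe events remains compatible with the results. On assumed equal observed rates between 10% and 85%, that excess is about 10 to 16 points at 75 per arm and 11 to 18 at 60 per arm. The finding of double-digit or near double-digit uncertainty does not depend on which rate in the range applies. For tolerability, even a clean result of 0/75 leaves 4.8% possible. The pain and opioid analyses and the sample size are unaffected.

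**What to change.** Replace the Aim 3 sentence in Section 10.0 with:

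> For Aim 3, the number and percentage of patients with at least one CTCAE grade 3 or 4 adverse event from the start of chemoradiation to the end-of-treatment visit will be reported by randomised arm, with the risk difference (Arm 2 minus Arm 1) and its 95% confidence interval (Newcombe or Miettinen-Nurminen; one to be named before analysis). The same will be reported excluding oral mucositis, so that background mucositis does not mask other harm. Post-treatment adverse events will be reported separately, because Arm 1 patients may start gabapentin then. Discontinuation of gabapentin due to side effects will be reported for Arm 2 only, with an exact 95% confidence interval and all patients randomised to Arm 2 as denominator.

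The count is of patients, not events, because toxicities are recorded again at every visit and one persisting toxicity could otherwise be counted repeatedly. The end-of-treatment visit needs one definition for this purpose: Section 5.6 allows the final radiotherapy visit or up to 2 weeks later, while the note under the study schedule in Section 6 places it 2 weeks after chemoradiation.

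The cost is a paragraph of text and a few lines of code, with no new patients, visits or data and no hypothesis test. The intervals will be wide, so the safety statement will read slightly less favourably than bare percentages would.
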